1 PROTOCOL SUMMARY

1.1 SYNOPSIS

Title: A phase II study of talimogene laherparepvec (T-VEC) in the treatment of recurrent cutaneous angiosarcoma

Study Description: Seventy-five percent of cutaneous angiosarcoma (CA) patients will eventually fail systemic therapy, and relapsed/refractory patients are left with no known efficacious treatment options. We hypothesize that direct treatment of CA lesions with T-VEC will stimulate local antitumor response, leading to objective responses and prevention of recurrence among enough patients to make this a viable treatment option for the affected population.

Objectives:

Primary Objective: To evaluate the efficacy of T-VEC as treatment for relapsed/refractory cutaneous angiosarcoma

Secondary Objectives:

1. To establish duration of response among treated patients that demonstrate response
2. To measure the duration of progression-free survival among treated patients
3. To measure the complete response rate for lesions that have complete clinical regression following study treatment
4. To monitor adverse events following administration of T-VEC injections
5. To measure the rate of patients requiring surgical resection of T-VEC–treated lesions

Tertiary/Exploratory Objectives:

1. To measure the degree of immune infiltration in surgically resected T-VEC–treated tumors
2. To evaluate surgical outcomes for those patients whose T-VEC–treated tumors are resected

Endpoints:

Primary Endpoint: Overall response rate: the proportion of patients to demonstrate complete or partial responses in injected lesions per modified RECIST criteria appropriate for cutaneous neoplasms.

Secondary Endpoints:

1. Response duration will be measured from the time of initial partial response or complete response until documented progression

2. Progression-free survival: period from time of first injection to progression of disease or appearance of new cutaneous angiosarcoma tumors that were not present at the time of study entry
3. Complete Response rate: proportion of patients with CR, defined as lesions with complete clinical regression
4. Incidence of adverse events from injection of T-VEC into cutaneous angiosarcoma
5. Proportion of patients whose T-VEC–treated tumors require surgical resection

Tertiary/Exploratory Endpoints:

1. Immunohistochemistry and flow cytometry analyses of immune infiltration within resected tumor specimens

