1.2 SCHEMA

1.3 SCHEDULE OF ACTIVITIES (SOA)

For explanation of procedures, please see Section 8 (Study Assessments and Procedures).

Baseline evaluations are to be conducted within 1 week prior to start of protocol therapy. Imaging must be done within 4 weeks prior to the start of therapy and then every three months starting at week 12. In the event that the patient's condition is deteriorating, laboratory evaluations should be repeated within 48 hours prior to initiation of the next cycle of therapy.

Table 1: Schedule of Activities

	Wk -4	Wk -1	Wk 1	Wk 2	Wk 3	Wk 4 and Bi-weekly	Wk 12 and every three months	Off Study ^e
T-VEC ^a			X			X	X	
Informed consent		X						
Demographics		X						
Medical history		X						
Concurrent meds		X	X	X	X	X	X	X
Physical exam		X	X			X	X	X
Imaging	X						X	
Vital signs		X	X	X	X	X	X	X
Height		X						
Weight		X	X	X	X	X	X	X
Performance status		X	X			X	X	X
Complete blood panel w/diff, platelets		X	X			X	X	X
CMP ^b		X	X			X	X	X
EKG		X						
Coagulation studies (PT/PTT/INR)		X						
Adverse event evaluation		X	X	X	X	X	X	X
Tumor measurements – ruler/calipers and digital photography of lesions		X	X	X	X	X	X	X
Punch biopsy ^c		X						X
B-HCG blood pregnancy test		X ^d						

a. Talimogene laherparepvec (T-VEC): Dose as assigned; *administration schedule only applies if tumor is visualized*. Dose 2 to be given 21 days after dose 1 with window of +3 days. Window for remaining doses is +/- 3 days.

b. Comprehensive Metabolic Panel: Albumin, alkaline phosphatase, total bilirubin, bicarbonate, BUN, calcium, chloride, creatinine, glucose, , potassium, total protein, SGOT [AST], SGPT [ALT], sodium.

c. Punch biopsy will be performed using a 4-6 mm punch, up to 2 biopsies per instance.

d. Serum pregnancy test (women of childbearing potential) completed within 72 hours of enrollment.

e. Patients will be treated for a maximum of 52 weeks per section 6.1.2.3. Off-study treatment evaluation should be completed within 30 days after last T-VEC treatment. Patients will continue to be followed-up posttreatment to determine RFS and note any complications; patients will also be followed every 6 months (+/- 1 month) for 2 years by telephone, review of follow-up notes for recurrence status and latent herpetic infection.

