2.2 BACKGROUND

2.2.1 DISEASE BACKGROUND

CA is a rare cutaneous neoplasm that is classified as a soft tissue sarcoma which arises within the epidermis or dermis. The disease presents largely as 2 separate phenotypes. In one form, the cause is idiopathic and effects elderly men with a predilection for occurrence in the head and neck region. In another form, the disease is associated with a history of radiation therapy and most commonly affects women, with disease occurring in the skin of the breast after breast conservation therapy for primary breast cancer. The latter form occurs with a median latency period of 7 years between the exposure to radiation and development of a secondary malignancy.

Treatment for either condition is primarily wide surgical resection. Wide margins can be difficult to obtain as anatomic constraints often limit the resection. Even when primary resection is feasible, recurrence is common, with a local recurrence rate up to 60% for those with idiopathic cutaneous angiosarcoma and 75% for those with radiation-associated cutaneous angiosarcoma. Complicating treatment further is the presence of multifocal disease in both the primary and recurrent setting, which is difficult to manage with surgical resection. Despite the known association, radiation therapy has been advocated for cutaneous angiosarcoma as a way to increase local control.

With high local recurrence rates, there is an unmet need for local therapy. The anatomic constraints limiting resection in the primary setting are worse with recurrence and repeat radiation therapy to a site is generally not feasible. Systemic therapy is used for these patients; however, these options are often restricted by the limitations associated with the age of these often elderly patients.

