8 STUDY ASSESSMENTS AND PROCEDURES

8.1 EFFICACY ASSESSMENTS

8.1.1 PRE-STUDY PROCEDURES

To be performed no more 4 weeks prior to initiation of study treatment

Imaging: CT chest, abdomen, and pelvis with IV contrast

To be performed within 1 week of 1st study treatment evaluation

Informed consent, demographics, concomitant medications, performance status, physical examination, vitals, height, weight, complete blood count, complete metabolic panel, serum pregnancy test completed within 72 hours of enrollment, serum HSV1 Ab, electrocardiogram, tumor measurement by palpation/exam, request slides from tumor biopsies for immunohistochemical analysis.

Week 1 procedures:

Complete blood count, complete metabolic panel, pharmacy to begin thawing/preparation of dose, clinic visit with concurrent medications, performance status, physical examination, vitals, weight, tumor measurement by examination, injection of T-VEC into primary tumor.

Weeks 2, 3 and 6:

Clinic visit with concurrent medications, performance status, physical examination, vitals, weight, anti-HSV Ab titer on week 6 only

Bi-weekly procedures starting Week 4-week 52:

Complete blood count, complete metabolic panel, pharmacy to begin thawing/preparation of dose, clinic visit with concurrent medications, performance status, physical examination, vitals, weight, tumor measurement by examination, injection of T-VEC into primary tumor.

Off-study procedures:

Complete blood count, complete metabolic panel, clinic visit with concurrent medications, performance status, physical examination, vitals, weight, and punch biopsy all within 30 days of last study treatment. Follow up of any treatment-related adverse events until resolution, stabilization, or death for a minimum of 30 days after last study treatment. Data on any perioperative complications should be also collected as applicable. Final tumor

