8.1.2.1 DEFINITIONS

Evaluable for toxicity. All patients will be evaluable for toxicity from the time of their first treatment with T-VEC

Evaluable for objective response. Only those patients who have measurable disease present at baseline, have received at least three injections at the 10^8 dose level, and have had their disease re-evaluated will be considered evaluable for response. These patients will have their response classified according to the definitions stated below.

Evaluable Non-Target Disease Response. Patients who have lesions present at baseline that are evaluable but do not meet the definitions of measurable disease, have received at least one cycle of therapy, and have had their disease re-evaluated will be considered evaluable for non-target disease. The response assessment is based on the presence, absence, or unequivocal progression of the lesions.

Disease Parameters

Measurable disease. Measurable lesions are defined as those that can be accurately measured in at least one dimension (longest diameter to be recorded) as ≥ 6 mm by calipers on clinical examination. All tumor measurements must be recorded in millimeters (or decimal fractions of centimeters).

Non-measurable disease. All other lesions (or sites of disease), including small lesions (longest diameter < 6 mm) are considered non-measurable disease.

Note: Cystic lesions that meet the criteria for radiographically defined simple cysts should not be considered as malignant lesions (neither measurable nor non-measurable) since they are, by definition, simple cysts.

“Cystic lesions” thought to represent cystic metastases can be considered as measurable lesions if they meet the definition of measurability described above. However, if non-cystic lesions are present in the same patient, these are preferred for selection as target lesions.

Target lesions. All measurable lesions up to a maximum of 5 lesions in total, representative of all involved organs, should be identified as **target lesions** and recorded and measured at baseline. Target lesions should be selected on the basis of their size (lesions with the longest diameter), but in addition should be those that lend themselves to

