reproducible repeated measurements. It may be the case that, on occasion, the largest lesion does not lend itself to reproducible measurement in which circumstance the next largest lesion that can be measured reproducibly should be selected. A sum of the diameters (longest for non-nodal lesions, short axis for nodal lesions) for all target lesions will be calculated and reported as the baseline sum diameters. The baseline sum diameters will be used as reference to further characterize any objective tumor regression in the measurable dimension of the disease. All target lesions will also be injected lesions.

Non-target lesions. All other lesions (or sites of disease) including any measurable lesions over and above the 5 target lesions should be identified as **non-target lesions** and should also be recorded at baseline. Measurements of these lesions are not required, but the presence, absence, or in rare cases unequivocal progression of each should be noted throughout follow-up. All non-target lesions will not be injected with T-VEC.

Methods for Evaluation of Measurable Disease

All measurements should be taken and recorded in metric notation using a ruler or calipers. All baseline evaluations should be performed as closely as possible to the beginning of treatment and never more than 4 weeks before the beginning of the treatment.

Clinical lesions. Clinical lesions will only be considered measurable when they are superficial (e.g., skin nodules and palpable lymph nodes) and ≥ 6 mm diameter as assessed using calipers. Documentation by color photography at baseline, including a ruler to estimate the size of the lesion, is recommended.

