8.1.2.3 RESPONSE CRITERIA

Evaluation of Target Lesions

Complete Response (CR): Disappearance of all target lesions.

Partial Response (PR): At least a 30% decrease in the sum of the diameters of target lesions, taking as reference the baseline sum diameters.

Progressive Disease (PD): At least a 20% increase in the sum of the diameters of target lesions, taking as reference the smallest sum on study (this includes the baseline sum if that is the smallest on study). (Note: the appearance of one or more new lesions is also considered progression).

Stable Disease (SD): Neither sufficient shrinkage to qualify for PR nor sufficient increase to qualify for PD, taking as reference the smallest sum diameters while on study.

Evaluation of Non-Target Lesions

Complete Response (CR): Disappearance of all non-target lesions and normalization of tumor marker level.

Progressive Disease (PD): Appearance of one or more new lesions and/or unequivocal progression of existing non-target lesions. Unequivocal progression should not normally trump target lesion status. It must be representative of overall disease status change, not a single lesion increase.

Although a clear progression of “non-target” lesions only is exceptional, the opinion of the treating physician should prevail in such circumstances, and the progression status should be confirmed at a later time by the review panel (or Principal Investigator). Photography of these changes is recommended.

Evaluation of Best Overall Response

The best overall response is the best response recorded from the start of the treatment until disease progression/recurrence (taking as reference for progressive disease the smallest measurements recorded since the treatment started). The patient's best response assignment will depend on the achievement of both measurement and confirmation criteria.

Overall Response Criteria

Target Lesions	Non-Target Lesions	New Lesions	Overall Response	Best Overall Response when Confirmation is Required
CR	CR	No	CR	≥ 4 wk Confirmation
CR	Non-CR/Non-PD	No	PR	≥ 4 wk Confirmation
CR	Not evaluated	No	PR	
PR	Non-CR/Non-PD/not evaluated	No	PR	
SD	Non-CR/Non-PD/not evaluated	No	SD	Documented at least once ≥ 4 wk from baseline
PD	Any	Yes or No	PD	No prior SD, PR, or CR
Any	PD***	Yes or No	PD	
Any	Any	Yes	PD	

*** In exceptional circumstances, unequivocal progression in non-target lesions may be accepted as disease progression.

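### Complete response of non-target lesions is tied to a tumor marker that the protocol neither names nor measures; this is a minor error that can only lower the descriptive CR rate, and only if the response criteria are followed literally

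*Combined protocol and SAP*

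**What the plan says.** - **Response criteria (8.1.2.3).** Target CR is the disappearance of all target lesions. Non-target CR carries a second condition: "Disappearance of all non-target lesions and normalization of tumor marker level". In the overall response table, CR requires CR in both target and non-target lesions. Target CR with non-target status Non-CR/Non-PD, or not evaluated, gives PR.
- **Laboratory tests (1.3 and 8.1.1).** Table 1 lists blood counts, a chemistry panel, coagulation studies and a pregnancy test. The panel is itemised ("Comprehensive Metabolic Panel: Albumin, alkaline phosphatase, total bilirubin, bicarbonate, BUN, calcium, chloride, creatinine, glucose", then potassium, total protein, the transaminases and sodium). Section 8.1.1 adds HSV antibody tests. The bi-weekly visits begin with "Complete blood count, complete metabolic panel, pharmacy to begin thawing/preparation of dose, clinic visit with concurrent medications", followed by examination and tumor measurement. No analyte is designated a tumor marker.
- **Definitions (8.1.2.1).** On evaluable non-target disease: "The response assessment is based on the presence, absence, or unequivocal progression of the lesions". The non-target group is broad: "All other lesions (or sites of disease) including any measurable lesions over and above the 5 target lesions should be identified as" non-target lesions. It also takes in lesions under 6 mm, which are non-measurable. The section adds: "All non-target lesions will not be injected with T-VEC".
- **Endpoint.** Secondary endpoint 3 in the Synopsis is the "proportion of patients with CR, defined as lesions with complete clinical regression". Table 2 (Section 3) gives the same clinical definition but labels it pCR.

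**The concern.** A criterion with two parts joined by *and* is met only when both are shown. Here the second part rests on a measurement that the trial does not make. An assessor who applies 8.1.2.3 as written cannot document non-target CR, even when every lesion has gone. An assessor who applies 8.1.2.1 or the Synopsis can. The same patient may therefore be CR or PR according to which section is opened, and the plan has no rule for choosing.

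At stake are the CR rate, a listed secondary endpoint, and the duration of overall CR defined in 8.1.2.4, which starts from the same call. Section 2.2.1 makes non-target lesions plausible in this population: "Complicating treatment further is the presence of multifocal disease in both the primary and recurrent setting". The trial is open label, so a scoring rule settled after responses are known could look driven by the outcome.

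**Working it through.** **1. Can the marker condition be met?** The tests in Table 1 and 8.1.1 are blood counts, chemistry, coagulation, pregnancy test and HSV antibody. No marker, threshold or sampling time is given anywhere. The condition cannot be evaluated.

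**2. What does the table then return?** Take a patient with baseline non-target lesions whose target and non-target lesions have all disappeared, with no new lesions.

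| How the unmeasured marker is treated | Non-target status | Overall response |
|---|---|---|
| Not shown to be normal | Non-CR/Non-PD | PR |
| Missing | Not evaluated | PR |
| Condition ignored, lesions only (8.1.2.1) | CR | CR |

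Both literal readings give PR. CR is reached only by setting the marker condition aside. The condition can remove CRs but never add them.

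**3. Who can be affected?** Only patients who had a non-target lesion at baseline and whose lesions all disappear, including the uninjected ones. If an uninjected lesion persists, the table gives PR with or without the marker condition.

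**4. Does it reach the primary analysis?** First, the plan's own figures (Section 9.2: 8 then 13 patients, stop at 1 or fewer responses, reject the treatment at 3 or fewer, P0 = 0.10, P1 = 0.40):

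- Early termination under P0 = 0.9^8 + 8 × 0.1 × 0.9^7 = 0.8131 (stated 0.813).
- Expected sample size = 8 + (1 − 0.8131) × 5 = 8.93 (stated 8.93).
- P(conclude effective) = Σ over x = 2 to 8 of P(X1 = x) × P(X2 ≥ 4 − x), with X1 ~ Bin(8, p) and X2 ~ Bin(5, p). At p = 0.10 this is 0.0307 (stated 0.031). At p = 0.40 it is 0.8015, so the type II error is 0.1985 (stated 0.198).

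The design reproduces. Its count is CR + PR, so a patient moved from CR to PR is still a responder and every figure above stays the same.

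**5. How far can the CR rate move?** One patient in 13 is 1/13 = 7.7 percentage points. Let q be the true CR rate and f the share of complete responders who had a non-target lesion at baseline. The documents give neither. Under the literal reading, scored CR rate = q(1 − f). With q = 0.20 assumed:

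| f | Scored CR rate | Expected CRs in 13 |
|---|---|---|
| 0 | 0.20 | 2.6 |
| 0.25 | 0.15 | 1.95 |
| 0.50 | 0.10 | 1.3 |
| 0.75 | 0.05 | 0.65 |
| 1.00 | 0.00 | 0 |

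At f = 0.50, assumed q of 0.10 and 0.30 give 0.05 and 0.15. In whole patients: if 3 of 13 cleared all disease (23.1%, exact 95% interval 5.0% to 53.8%) and 1, 2 or 3 of them had a non-target lesion, the scored rate is 2/13 = 15.4%, 1/13 = 7.7% or 0/13 = 0% (the last with interval 0% to 24.7%). These counts are illustrations. Without the marker condition the scored rate is q in every row.

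**6. Other endpoints.** Overall duration of response (8.1.2.4) starts at CR or PR, whichever comes first. Progression-free survival (8.1.2.5) does not use the CR label. Neither changes.

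**The case against.** A reader might infer that no patient with a non-target lesion can ever be scored CR, and that the CR rate is therefore biased down. The documents do not support that, for three reasons.

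- Nothing says that an unmeasured marker counts as abnormal. Section 8.1.2.1 bases non-target assessment on the lesions alone, and an assessor following it would record CR once they are gone.
- Secondary endpoint 3 has its own definition, complete clinical regression, with no marker condition and no reference to the response table. Under that definition the marker has no effect. Bias requires that CR be taken from 8.1.2.3 and that its marker condition be enforced.
- Non-target lesions are not injected, so the affected group is limited to patients whose uninjected lesions also disappear. The remark on multifocal disease does not size that group, because up to five measurable lesions are targets.

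It is also fair to say that the secondary endpoints are descriptive, that duration of overall CR is not a listed endpoint in the Synopsis or Table 2, and that no decision rule turns on this.

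All of that stands and limits the point. It does not remove it. Section 8.1.2.1 does not say that it overrides 8.1.2.3, and it refers patients evaluable for objective response to the definitions that follow. Endpoint 3 does not say which lesions must regress for a patient to count, and Section 9.4.3 adds no rule. The only patient-level algorithm in the document is the one that carries the marker condition.

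**Conclusion.** Wrong as written, but minor. The marker condition in 8.1.2.3 cannot be applied and conflicts with 8.1.2.1 and with the clinical-regression definition in the Synopsis and Table 2. Followed literally, it scores a patient whose target and non-target lesions have all disappeared as PR.

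The error runs in one direction: 7.7 percentage points off the CR rate for each reclassified patient in 13, and the loss of that patient from the duration of overall CR. The conclusion is conditional on CR being taken from the 8.1.2.3 criteria and table. The number affected is not given and may be zero, so a downward bias is possible but not established. The primary endpoint and its error rates are untouched.

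**What to change.** In 8.1.2.3, delete the tumor-marker condition so that non-target CR is the disappearance of all non-target lesions. This brings the criteria into line with 8.1.2.1.

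Deletion alone does not settle the endpoint. In the Synopsis, Table 2 and Section 9.4.3, also:

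- state that the CR rate in secondary endpoint 3 is scored by complete clinical regression;
- specify whether it uses injected (target) lesions only or the overall response table;
- use one label, since the Synopsis says CR and Table 2 says pCR for the same clinical definition.

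The cost is a few words in a protocol amendment, with no new data, visits or patients. It should be made before responses are scored.

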8.1.2.4 DURATION OF RESPONSE

Duration of Response

Duration of overall response: The duration of overall response is measured from the time measurement criteria are met for CR or PR (whichever is first recorded) until the first date that recurrent or progressive disease is objectively documented (taking as reference for progressive disease the smallest measurements recorded since the treatment started).

The duration of overall CR is measured from the time measurement criteria are first met for CR until the first date that progressive disease is objectively documented.

Duration of stable disease: Stable disease is measured from the start of the treatment until the criteria for progression are met, taking as reference the smallest measurements recorded since the treatment started, including the baseline measurements.

